4.6.2. Benefit Assessment

Benefit considerations for each individual subject may include:

- Potential benefit of receiving FF/VI combined inhaled therapy during the study
- Contributing to the process of developing new asthma therapies
- Medical evaluations/assessments associated with study procedures e.g. PEF, FEV₁, physical examinations and vital signs.

4.6.3. Overall Benefit:Risk Conclusion

The study is considered low risk. The dose of FF/VI to be used in this study (100/25mcg) is an approved dose world-wide and has been administered on an out-patient basis in phase III studies in both asthma and COPD and was well tolerated. The asthma patients to be included in this study are comparable to those in the asthma phase III studies. Taking into account the measures taken to minimise risk to patients participating in this study, the potential low risks identified in association with inhaled FF/VI are justified by the anticipated benefits that will be afforded to subjects with asthma.

5. SELECTION OF STUDY POPULATION AND WITHDRAWAL CRITERIA

Specific information regarding warnings, precautions, contraindications, adverse events (AEs), and other pertinent information on the GSK investigational product or other study treatment that may impact subject eligibility is provided in the BREO ELLIPTA datasheet on the New Zealand Medsafe website:

<http://www.medsafe.govt.nz/profs/datasheet/b/breoelliptainhalation.pdf>.

Deviations from inclusion and exclusion criteria are not allowed because they can potentially jeopardize the scientific integrity of the study, regulatory acceptability or subject safety. Therefore, adherence to the criteria as specified in the protocol is essential.

5.1. Inclusion Criteria

A subject will be eligible for inclusion in this study only if all of the following criteria apply:

| AGE |
|--|
| 1. Age of subject: Between 18 and 65 years of age inclusive, at the time of signing the informed consent. |

| TYPE OF SUBJECT AND DIAGNOSIS INCLUDING DISEASE SEVERITY |
|---|
| 2. Asthma: A doctor diagnosis of asthma for at least 6 months prior to the start of the study. |
| 3. Severity of disease: A screening pre-bronchodilator FEV ₁ ≥ 60% of predicted |

NOTE: Predicted values will be based upon NHANES III [[Hankinson, 1999](#)]

4. Reversibility of disease:

Demonstrated presence of reversible airway disease at screening (repeat testing of eligibility can be undertaken following the screening visit up to Day -7).

OR

The presence of reversible airways disease can have been demonstrated historically within 6 months of the screening visit.

NOTE: Reversible airway disease is defined as increase in FEV₁ of $\geq 12\%$ over baseline and an absolute change of ≥ 200 mL within 30 minutes following 4 inhalations of albuterol/salbutamol inhalation aerosol/spacer (or equivalent nebulised treatment with albuterol/salbutamol solution).

5. Current Therapy:

- Short-Acting Beta2-Agonists (SABA): prescribed SABA for at least 12 weeks prior to screening.

No ICS, LABA, long acting muscarinic antagonist (LAMA), leukotriene receptor antagonist (LTRA) therapy for three months prior to the start of the study.

6. Non-smoker or ex-smoker (no smoking in previous 12 weeks, ≤ 10 pack years).

7. Screening and Day -7 AM FeNO values > 40 ppb.

NOTE: Both screening and Day -7 AM FeNO values for Treatment Period 1 need to be > 40 ppb for the subject to be eligible.

WEIGHT

8. **Bodyweight and BMI:** Bodyweight ≥ 50 kg and Body Mass Index (BMI) within the range 18.0-40.0 kg/m² (inclusive)

SEX

9. Male OR Female

Females:

A female subject is eligible to participate if she is not pregnant (as confirmed by a negative urine human chorionic gonadotrophin (hCG) test), not lactating, and at least one of the following conditions applies: Non-reproductive potential defined as:

- Pre-menopausal females reporting one of the following:
 - Tubal ligation
 - Hysteroscopic tubal occlusion procedure with follow-up confirmation of bilateral tubal occlusion
 - Hysterectomy

| |
|--|
| 
 • Bilateral Oophorectomy • Postmenopausal defined as 12 months of spontaneous amenorrhea [in questionable cases a blood sample with simultaneous follicle stimulating hormone (FSH) and estradiol levels consistent with menopause (refer to laboratory reference ranges for confirmatory levels)]. Females on hormone replacement therapy (HRT) and whose menopausal status is in doubt will be required to use one of the highly effective contraception methods if they wish to continue their HRT during the study. Otherwise, they must discontinue HRT to allow confirmation of post-menopausal status prior to study enrolment. 
b. Reproductive potential and agrees to follow one of the options listed in the Modified List of Highly Effective Methods for Avoiding Pregnancy in Females of Reproductive Potential (FRP) (see Appendix 3) from 30 days prior to the first dose of study medication and until after the last dose of study medication and completion of the follow-up visit.
 
The investigator is responsible for ensuring that subjects understand how to properly use these methods of contraception.
 |
|--|

| |
|------------------|
| INFORMED CONSENT |
|------------------|

| |
|--|
| 10. Capable of giving signed informed consent, which includes compliance with the requirements and restrictions listed in the consent form and in this protocol. |
|--|

5.2. Exclusion Criteria

A subject will not be eligible for inclusion in this study if any of the following criteria apply:

| |
|---------------------------------------|
| CONCURRENT CONDITIONS/MEDICAL HISTORY |
|---------------------------------------|

1. A history of life-threatening asthma.

NOTE: Life-threatening asthma is defined as an asthma episode that required intubation and/or was associated with hypercapnia, respiratory arrest or hypoxic seizures within the last 5 years

2. Other significant pulmonary diseases to include (but not limited to): pneumonia, pneumothorax, atelectasis, pulmonary fibrotic disease, bronchopulmonary dysplasia, chronic bronchitis, emphysema, chronic obstructive pulmonary disease, or other respiratory abnormalities other than asthma.

3. Respiratory Infection: Culture-documented or suspected bacterial or viral infection of the upper or lower respiratory tract, sinus or middle ear that is not resolved within 4 weeks of screening that:

- led to a change in asthma management

OR

- in the opinion of the Investigator, is expected to affect the subject's asthma status OR

the subject's ability to participate in the study.

However, subjects can be rescreened to allow for an adequate time period (of at least 4 weeks) between resolution of the infection and the date of randomisation.

- 4. Asthma Exacerbation:** Any asthma exacerbation requiring oral corticosteroids within 12 weeks of screening or that resulted in overnight hospitalization requiring additional treatment for asthma within 6 months prior to screening.

CONCOMITANT MEDICATIONS

- 5. Concomitant Medications:** These are listed in detail in Section 6.9 of the protocol. Restrictions of nitrate-rich foods are listed in detail in Section 6.9.1.1 of the protocol.

RELEVANT HABITS

- 6. Tobacco Use:** Current smokers or a smoking history of ≥ 10 pack years. A subject may not have used any inhaled tobacco products in 12 weeks preceding the screening visit.

CONTRAINDICATIONS

- 7. Previous Participation:** Exposure to more than four new chemical entities within 12 months prior to the first dosing day.

DIAGNOSTIC ASSESSMENTS AND OTHER CRITERIA

- 8. Other concurrent Diseases/Abnormalities:** A subject has any clinically significant, uncontrolled condition or disease state that, in the opinion of the investigator, would put the safety of the subject at risk through study participation or would confound the interpretation of the study results if the condition/disease exacerbated during the study.

The list of additional excluded conditions/diseases includes, but is not limited to the following:

| | |
|---|---|
| Congestive heart failure | Known aortic aneurysm |
| Clinically significant coronary heart disease | Clinically significant cardiac arrhythmia |
| Stroke within 3 months of Visit 1 | Uncontrolled hypertension* |
| Recent or poorly controlled peptic ulcer | Haematologic, hepatic**, or renal disease |
| Immunologic compromise | Current malignancy*** |
| Tuberculosis (current or untreated)**** | Cushing's disease |
| Addison's disease | Uncontrolled diabetes mellitus |
| Liver cirrhosis | Systemic Lupus Erythematosus |
| Uncontrolled thyroid disorder | Recent history of drug or alcohol abuse |

*Two or more measurements with systolic BP>160mmHg, or diastolic BP >100mmHg

**Subjects with chronic stable hepatitis B and C are acceptable provided their screening ALT is < 2x upper limit of normal (ULN) and the subject otherwise meets the entry criteria. Subjects who have chronic co-infection with both hepatitis B and hepatitis C are not eligible.

***history of malignancy is acceptable only if subject has been in remission for one year prior to Visit 1 (remission = no current evidence of malignancy and no treatment for the malignancy in the 12 months prior to Visit 1)

****Subjects with a history of tuberculosis infection who have completed an appropriate course of antituberculous treatment may be suitable for study entry provided that there is no clinical suspicion of active or recurrent disease.

9. Oropharyngeal examination: A subject will not be eligible if he/she has clinical visual evidence of oral candidiasis at screening.

10. Pregnancy and Lactating Females:

- Pregnant females as determined by positive serum hCG test at screening or by positive urine hCG test prior to dosing.
- Lactating females

11. Allergies:

- **Milk Protein Allergy:** History of severe milk protein allergy.
- **Drug Allergy:** Any adverse reaction including immediate or delayed hypersensitivity to any beta₂-agonist, sympathomimetic drug, or any intranasal, inhaled, or systemic corticosteroid therapy. Known or suspected sensitivity to the constituents of the Dry Powder Inhaler (DPI) (i.e., lactose or magnesium stearate).
- **Historical Allergy:** History of drug or other allergy that, in the opinion of the investigator or GSK Medical Monitor, contraindicates their participation.

5.3. Screening Failures

Screen failures are defined as subjects who consent to participate in the clinical trial but are never subsequently randomized. In order to ensure transparent reporting of screen failure subjects, meet the Consolidated Standards of Reporting Trials (CONSORT) publishing requirements, and respond to queries from Regulatory authorities, a minimal set of screen failure information is required including Demography, Screen Failure details, Eligibility Criteria, and Serious Adverse Events (SAEs) (see Section 7.4.1.6).

Subjects who initially fail screening based on not meeting one of the inclusion/exclusion criteria may be rescreened subsequently. A limited rescreen checking this parameter against the inclusion/exclusion criteria may be performed, and if the subject then meets all the eligibility criteria, they would be allowed to be enrolled onto the study. However, repeat Day -7 visits cannot be performed.

5.4. Withdrawal/Stopping Criteria

Worsening asthma: The following criteria will be used to aid the Investigator in determining asthma stability. A randomised subject who meets any of the following stopping criteria will be withdrawn from the study:

- Clinic PEF and FEV₁ below the stability limit values calculated at pre-treatment Day 1, Treatment Period 1. Subjects must have completed a minimum of at least 10 out of 14 peak flow measurements during the one week prior to randomisation (Day -7 to Day 1).
- During the study, the subject experienced:
 1. At least 4 consecutive days in which the PEF (either AM, PM or both) has fallen below the PEF Stability Limit calculated at pre-treatment Day 1, Treatment Period 1 OR
 2. At least 3 days in which ≥ 12 inhalations/day of albuterol/salbutamol were used.
- Subjects who experience a protocol-defined severe exacerbation, defined as deterioration of asthma requiring the use of systemic corticosteroids (tablets, suspension, or injection) for at least 3 days or an in-patient hospitalization or emergency department visit due to asthma that required systemic corticosteroids.
- Clinical asthma worsening which in the opinion of the investigator requires additional asthma treatment other than study medication or study supplied albuterol/salbutamol.

The following actions must be taken in relation to a subject who fails to attend the clinic for a required study visit:

- The site must attempt to contact the subject and re-schedule the missed visit as soon as possible.
- The site must counsel the subject on the importance of maintaining the assigned visit schedule and ascertain whether or not the subject wishes to and/or should continue in the study.
- In cases where the subject is deemed 'lost to follow up', the investigator or designee must make every effort to regain contact with the subject (where possible, 3 telephone calls and if necessary a certified letter to the subject's last known mailing address or local equivalent methods). These contact attempts should be documented in the subject's medical record.
- Should the subject continue to be unreachable, only then will he/she be considered to have withdrawn from the study with a primary reason of "Lost to Follow-up".

A subject may withdraw from study treatment at any time at his/her own request, or may be withdrawn at any time at the discretion of the investigator for safety, behavioural or administrative reasons. If a subject withdraws from the study, he/she may request destruction of any samples taken, and the investigator must document this in the site study records.

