3. OBJECTIVE(S) AND ENDPOINT(S)

| Objectives | Endpoints |
|--|--|
| Primary | |
| 
 To characterise the fraction of exhaled nitric oxide (FeNO) time profile following repeat administration of fluticasone furoate/vilanterol (FF/VI) 100/25mcg combination in comparison with placebo in subjects with asthma. | 
 Change from baseline FeNO over time following the cessation of repeat dose treatment with FF/VI. |
| Secondary | |
| 
 Change in FeNO over the treatment period following repeat administration of FF/VI 100/25mcg combination in comparison with placebo in subjects with asthma. To determine the Peak Expiratory Flow (PEF) during and following repeat administration of FF/VI 100/25mcg combination in comparison with placebo in subjects with asthma. To determine FEV₁ following repeat administration of FF/VI 100/25mcg combination in comparison with placebo in subjects with asthma | 
 Change from baseline FeNO over the FF/VI treatment period. Measurement of PEF during treatment and following cessation of repeat dose treatment with FF/VI. Measurement of FEV₁ pre-treatment and for up to 7 days after cessation of repeat dose treatment with FF/VI. |
| Exploratory | |
| 
 To investigate the effect of repeat administration of FF/VI 100/25mcg combination on exploratory biomarkers, including but not limited to, blood eosinophil levels and serum periostin levels, in comparison with placebo in subjects with asthma. | 
 Measurement of exploratory biomarkers, including but not limited to, blood eosinophil and serum periostin levels at baseline, and at various time points after cessation of repeat dose treatment with FF/VI. |

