4.6.1. Risk Assessment

| Potential Risk of Clinical Significance | Mitigation Strategy | Monitoring implemented |
|--|---|---|
| Investigational Product (IP) | | |
| There is a potential risk of worsening asthma as subjects will receive placebo in one treatment arm and no treatments during the washout periods (however access to SABA rescue medication will be available throughout the entire study). | Stopping criteria will be applied for both FEV ₁ (during the clinic stays/visits) and PEF (out-patient and in-clinic) which will be monitored throughout the study treatment and washout periods. | Stopping criteria will be applied for both FEV ₁ (during the clinic stays) and PEF (out-patient and in-clinic) which will be monitored throughout the study treatment and washout periods. |
| As with any inhaled medication paradoxical bronchospasm may occur with an immediate wheeze after dosing. | If bronchospasm occurs following dosing, immediate administration of a short-acting (i.e., quick relief) inhaled bronchodilator (e.g., albuterol) is recommended. If this treatment fails to provide relief, a physician should be contacted immediately and/or emergency treatment should be sought. | First dose of the study medication in each treatment period will be administered in the clinic under the supervision of a physician. |
| FF/VI is contraindicated in subjects with severe milk protein allergy or known hypersensitivity or any ingredient of the preparation. | These subjects will be excluded from the study. | Not applicable. |
| Cardiovascular effects, such as cardiac arrhythmias e.g. supraventricular tachycardia and extrasystoles may be seen with sympathomimetic drugs, including fluticasone furoate/vilanterol. Therefore fluticasone furoate/vilanterol should be used with caution in patients with severe cardiovascular disease. | Caution is needed in patients with pre-existing cardiovascular (CV) disease, especially severe CV disease. Patients with severe CV disease will be excluded. | Not applicable |

| Potential Risk of Clinical Significance | Mitigation Strategy | Monitoring implemented |
|---|--|---|
| Investigational Product (IP) | | |

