6.3. Blinding

This will be a double-blind study and the following will apply.

- The investigator or treating physician may unblind a subject's treatment assignment **only in the case of an emergency OR in the event of a serious medical condition when knowledge of the study treatment is essential for the appropriate clinical management or welfare of the subject as judged by the investigator.**
- Investigators have direct access to the subject's individual study treatment.
- It is preferred (but not required) that the investigator first contacts the Medical Monitor or appropriate GSK study personnel to discuss options **before** unblinding the subject's treatment assignment.
- If GSK personnel are not contacted before the unblinding, the investigator must notify GSK as soon as possible after unblinding, but without revealing the treatment assignment of the unblinded subject, unless that information is important for the safety of subjects currently in the study.
- The date and reason for the unblinding must be fully documented in the CRF.

The patients, site staff and GSK will remain blinded for the duration of the study.

A subject will be withdrawn if the subject's treatment code is unblinded by the investigator or treating physician. The primary reason for discontinuation (the event or condition which led to the unblinding) will be recorded in the CRF.

- GSK's Global Clinical Safety and Pharmacovigilance (GCSP) staff may unblind the treatment assignment for any subject with an SAE. If the SAE requires that an expedited regulatory report be sent to one or more regulatory agencies, a copy of the report, identifying the subject's treatment assignment, may be sent to investigators in accordance with local regulations and/or GSK policy.

Sealed code break envelopes will be provided to the site, in case of unblinding.

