7.3.3.2. PEF below Stability Limit

Should the PEF fall below the PEF stability limit, the subject should contact the site. The investigator must monitor the subject and withdraw the subject if he/she meets any of the criteria in Section [5.4](#).

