11.7. Appendix 7: Premature Withdrawals & Handling of Missing Data

11.7.1. Premature Withdrawals

Element	Reporting Detail
General	
 • Subject study completion (i.e. as specified in the protocol) was defined as subject is one who has completed both treatment periods, all assessments up to Day 35 of both treatment periods, and all of the follow-up assessments. The end of the study is defined as the last subject's last visit. • Withdrawn subjects were not replaced in the study. • All available data from subjects who were withdrawn from the study will be listed and all available planned data will be included in summary tables and figures, unless otherwise specified.

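### FeNO observation stops when a subject meets a worsening-asthma criterion in the off-treatment window, although home readings could continue at little cost

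*Protocol*

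**What the plan says.** The primary endpoint (Protocol 3) is "Change from baseline FeNO over time following the cessation of repeat dose treatment with FF/VI". Protocol 4.1 collects it morning and evening for 21 days after treatment, to Day 35 of each period. The Time and Events Table (Protocol 7.1) puts the last dose on the morning of Day 14.

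Protocol 5.4 lists the worsening-asthma criteria and states the consequence: "A randomised subject who meets any of the following stopping criteria will be withdrawn from the study". One criterion is "At least 4 consecutive days in which the PEF (either AM, PM or both) has fallen below the PEF Stability Limit". The others concern clinic PEF and FEV1 below their limits, heavy rescue use on at least 3 days, a severe exacerbation, and worsening that needs added asthma treatment. For PEF, Protocol 7.3.3.2 repeats the instruction: "The investigator must monitor the subject and withdraw the subject if he/she meets any of the criteria in Section" 5.4. The risk table in Protocol 4.6.1 applies the FEV1 and PEF criteria, "which will be monitored throughout the study treatment and washout periods".

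On unblinding, Protocol 6.3 says: "A subject will be withdrawn if the subject's treatment code is unblinded by the investigator or treating physician". It does not say whether this means from treatment or from the study.

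SAP 11.7.1 says that for withdrawn subjects "all available planned data will be included in summary tables and figures". SAP 7.1.2 fits an MMRM with period, treatment, day, time, baseline terms and their interactions. SAP 11.7.2.3, headed as the section on missing data for statistical analysis, contains only a sentence on documenting excluded subjects. The sensitivity analyses in SAP 4.1 and 11.1 are optional and tied to protocol deviations.

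**The concern.** The aim is to describe how FeNO returns towards baseline once treatment stops. A subject whose airway function falls during that return leaves the study, and the FeNO curve ends there. The later part of each curve then rests more heavily on subjects who stayed stable.

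If the events that trigger withdrawal go with higher unobserved FeNO, the late means are too low. Losses after FF/VI would make suppression look longer-lasting. Losses in the placebo period would move the ratio towards 1. An MMRM handles this if the missing readings are missing at random given the modelled FeNO and baselines, but the triggers lie outside the model and the SAP neither states nor tests the assumption.

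The readings are easy to keep. Under Protocol 7.3.1 the subject has held the meter since Day -7.

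**Working it through.** **1. The plan's precision figure.** Inputs from Protocol 9.2.1: CVw 21.6%, 24 evaluable subjects, 95% interval.

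- sigma_w = sqrt(ln(1 + 0.216²)) = 0.2135
- Half-width = exp(t(0.975, n-2) × sigma_w × sqrt(2/n)) - 1
- n = 24: exp(2.074 × 0.2135 × 0.2887) - 1 = 13.6%, which matches the stated 14%.
- n = 20: exp(2.101 × 0.2135 × 0.3162) - 1 = 15.2%

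**2. Readings at stake.** Days 15 to 35, twice daily, give 21 × 2 = 42 readings per period. For a PEF fall that begins in the washout, the four-day rule means about 4 × 2 = 8 readings come first, so at most about 34 are lost by that route.

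**3. Bias, closed form (assumption-based).** Let p be the fraction withdrawn in one treatment and none in the other. Let rho be the correlation between the triggering worsening and unobserved log FeNO, given the FeNO already seen. Let SD be the residual SD of log FeNO. Then the downward shift in that treatment's late mean on the log scale is

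shift = rho × SD × phi(z) / (1 - p), where z is the (1 - p) normal quantile.

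With SD = 0.2135:

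| p | phi(z)/(1 - p) | rho 0.3 | rho 0.6 |
|---|---|---|---|
| 2/28 | 0.147 | 0.0094 (0.9%) | 0.0188 (1.9%) |
| 4/28 | 0.263 | 0.0169 (1.7%) | 0.0337 (3.4%) |
| 7/28 | 0.424 | 0.0271 (2.8%) | 0.0543 (5.6%) |

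The percentage is exp(shift) - 1. At the extreme, with SD 0.40, p = 7/28 and rho 0.6, it reaches 10.7%. It is zero when rho = 0, and also when both treatments lose equal fractions.

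**4. Bias, simulation (assumption-based).** The assumptions were 4,000 subjects per setting, an FF/VI effect of ln 0.5 at cessation, a median recovery half-time of 5 days, 7% or 14% withdrawn per period on PEF, and a PEF-inflammation correlation of 0.3 or 0.7. A likelihood model was fitted to FeNO only. The Day 28-35 mean was understated by 0.5-1.0% (weak correlation) to 1.1-2.7% (strong). The ratio shifted by about 0.5-3% if withdrawals fell in one treatment, and the shift largely cancelled if they were equal.

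**5. How those rates compare with the plan.** Over two periods, 7% gives 1 - 0.93² = 14% of subjects and 14% gives 1 - 0.86² = 26%. The plan's whole attrition allowance is 4/28 = 14.3%, and Protocol 4.4 expects low drop-out without giving a rate. The simulated rates are therefore on the high side.

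**6. What the MMRM can recover.** SAP 11.8.1 starts from an unstructured covariance. Over 42 time points that is 42 × 43 / 2 = 903 parameters, from at most 28 × 2 = 56 subject-periods. The named fallbacks are CSH and CS. Recovery of missing late readings through the covariance should not be relied on heavily.

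**7. Which pairs continued collection recovers.** A subject stopped in the Period 1 washout still receives no Period 2, so the pair is lost whatever is collected. Only a stop in the Period 2 washout yields a recovered pair. Most of the change from 13.6% to 15.2% therefore cannot be claimed as a gain.

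**The case against.** Several objections have force.

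- **Withdrawal in the washout does more than end FeNO collection.** A reader might infer otherwise because the period's dosing is over. But Protocol 6.10.2.1 prohibits controllers and oral steroids until after follow-up, and withdrawal releases a worsening subject from that. In the Period 1 washout it also prevents Period 2 dosing. This stands.
- **Continued collection is only a partial remedy.** Two of the four bulleted criteria in Protocol 5.4 involve new therapy, and usable off-treatment readings end when it starts. That cut is itself related to outcome. Subjects stopped during dosing are not helped. This also stands.
- **Informative missingness is not shown.** FeNO up to withdrawal is retained. Protocol 2.1 attributes single-dose bronchodilation mainly to VI, so a PEF fall after cessation may reflect loss of the bronchodilator rather than returning inflammation. Nothing ranks PEF above the other triggers. The point is therefore an unstated assumption, not a demonstrated bias.
- **Attrition is already allowed for.** The plan enrols 28 to obtain 24, and Protocol 4.3 and 6.2 permit replacement beyond 4 discontinuations. SAP 11.7.1 says withdrawn subjects were not replaced, which must be reconciled separately. The allowance protects precision but does not address who is lost.
- **The unblinding limb is weak.** One might infer that readings after a code break are discarded. Protocol 6.3 does not say so, does not say from the study, and limits unblinding to emergencies or serious conditions. Only the ambiguity remains.

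Protocol 5.4 also introduces its criteria as an aid to the investigator, which suggests some discretion, but the operative instruction is mandatory.

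**Conclusion.** The point holds as a minor, inexpensive improvement. Followed as written, the plan ends primary-endpoint observation in subjects who worsen off treatment, on triggers that the FeNO model does not contain, and without a stated missing-data assumption.

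The likely effect on the FF/VI:placebo ratio is roughly 0.5-3% if withdrawals fall mainly in one treatment, and near zero if they are balanced or unrelated to FeNO. That is small beside a half-width of about 14%. It rests on assumed withdrawal rates, correlations, residual SD and recovery time, none of which the documents supply. The larger values in the closed-form check need a quarter of subjects withdrawn in one treatment, or a residual SD well above the planned one.

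A reader might go further and conclude that the primary analysis is biased, or that continued collection would restore the planned precision. The documents support neither conclusion.

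**What to change.** Leave the stopping criteria, the care that follows and the consequences for further dosing unchanged.

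- **Protocol 5.4:** add that a subject who meets a criterion after the last dose of a period is asked to continue morning and evening home FeNO to Day 35 of that period, unless consent is withdrawn or the investigator judges it unsuitable. Record the start date of any new controller or corticosteroid. Reconcile this wording with the prohibition in Protocol 6.10.2.1.
- **SAP 11.7.2.3:** state that the primary model uses readings up to that start date, state the missing-at-random assumption, and add one sensitivity analysis, because cutting at new therapy remains related to outcome.
- **Protocol 6.3:** say whether withdrawal after unblinding ends FeNO collection.

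The cost is a short paragraph and a clarifying sentence in the protocol, a few lines in the SAP, and one extra analysis. The subject keeps the meter for up to 21 days and must return it for download. Where new therapy starts promptly, few readings will be gained.
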